6.4. Subset Analyses

No subset analyses will be performed.

6.5. Baseline and Other Summaries and Analyses

Data will be reported in accordance with the sponsor reporting standards.

6.5.1. Baseline Summaries

Demographics data (age, biological sex, race, ethnicity, weight, body mass index and height) will be summarized by group and overall, as outlined in Sections 5.2.1 and 5.2.2 as applicable.

6.5.2. Study Conduct and Participant Disposition

Participant evaluation groups will show end of study participant disposition by group and will show which participants were analyzed for pharmacokinetics and safety, which may not be produced in one table. Frequency counts and percentages will be supplied for participant discontinuation(s) by group.

6.5.3. Study Treatment Exposure

Not applicable.

6.5.4. Concomitant Medications and Nondrug Treatments

All prior and concomitant medication(s) as well as non-drug treatment(s) will be provided in listings.

6.6. Safety Summaries and Analyses

See Section 6.2.

7. INTERIM ANALYSES**7.1. Introduction**

No formal interim analysis will be conducted for this study. As this is an open-label study, the sponsor may conduct unblinded reviews of the data during the course of the study for the purpose of safety assessment, facilitating PK modeling, and/or supporting clinical development.

7.2. Interim Analyses and Summaries

Not applicable.

Appendix 1. Statistical Methodology Details

An example of SAS code for ANOVA:

```
proc mixed data = tab.pk;
  class group;
  model l&var = group /residual;
  lsmeans group/diff cl alpha=0.1;
  ods output lsmeans = lsmeans&var;
  ods output diffs=diffs&var;
run;
```

An example of SAS code for the PROC REG code for linear regression analyses:

```
proc reg data=tab.pk;
  model l&var=clcr/clb alpha=0.1;
  ods output ParameterEstimates = param&var;
  ods output FitStatistics = fit&var;
  ods output ANOVA = reg&var;
run;
```

An example of SAS code for stepwise regression with model selection using AIC:

```
proc glmselect data=tab.pk analysis plot=ALL;
  model pk_p = albumin age weight/ selection=stepwise (select = AIC stop = AIC)
    include=1 hierarchy=none showpvalues;
run;
```

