### **9.3.2.3. Supplementary Analyses**

Additional analysis using linear regression may be used to analyze the potential relationship between appropriate PK parameters (eg,  $AUC_{inf}$ ,  $AUC_{last}$ ,  $C_{max}$ ,  $f_u$ ,  $AUC_{inf,u}$ ,  $AUC_{last,u}$ ,  $C_{max,u}$ ) and hepatic function (eg, serum albumin concentration, PT or T bili). Plots of PK parameters (eg,  $AUC_{inf}$ ,  $AUC_{last}$ ,  $C_{max}$ ,  $f_u$ ,  $AUC_{inf,u}$ ,  $AUC_{last,u}$ ,  $C_{max,u}$ ) versus hepatic function will be constructed, with a regression line and 90% confidence region included. Estimates of the slope and intercept, together with a 90% CI, and the coefficient of determination (ie, R-squared and adj-R-squared) may be obtained from the model.

Additionally, as an exploratory analysis, age and body weight may be explored as additional covariates/factors in the models, as appropriate.

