### 10.7.3. Adverse Event Grading for Kidney Safety Laboratory Abnormalities

AE grading for decline in kidney function (ie, eGFR or eCrCl) will be according to KDIGO criteria.

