5.2.3. One-way Analysis of Variance (ANOVA)

The *one-way analysis of variance (ANOVA)* model will include group as a factor.

Estimates of the adjusted mean differences (Test - Reference), and corresponding 90% CIs, will be obtained from the model. These will be exponentiated to provide estimates of the ratio of adjusted geometric means (Test/Reference) and 90% CIs for the ratios. Example SAS code is given in Appendix 1.

Residuals from the models will be examined for normality and the presence of outliers via visual inspection of plots of residuals vs predicted values and normal probability plots of residuals but these will not be included in the clinical study report. If there are major deviations from normality or outliers (where studentized residuals are greater than 3 or less than - 3) then the effect of these on the conclusions may be investigated through alternative transformations and/or analyses excluding outliers. Justification for any alternative to the planned analysis will be given in the report of the study if applicable.

CCI

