5.2.4. Linear Regression PK Parameters versus Hepatic Function

Linear regression will be used to analyze the potential relationship between appropriate PK parameters (eg, AUC_{inf} , AUC_{last} , C_{max} , f_u , $AUC_{inf,u}$, $AUC_{last,u}$, $C_{max,u}$) and hepatic function as a continuous explanatory variable (using either continuous serum albumin, prothrombin time or total bilirubin, each modelled separately). Estimates of the slope and intercept, together

[figure not shown]
Pfizer Confidential

with a 90% CI, and the coefficient of determination (i.e. R-squared and adj-R-squared) may be obtained from the model. Example SAS code is given in Appendix 1.

Residuals from the models will be examined for normality and the presence of outliers via visual inspection of plots of residuals vs predicted values and normal probability plots of residuals but these will not be included in the clinical study report. If there are major deviations from normality or outliers (where studentized residuals are greater than 3 or less than - 3) then the effect of these on the conclusions may be investigated through alternative transformations and/or analyses excluding outliers. Alternative model structure may also be considered. Justification for any alternative to the planned analysis will be given in the report of the study if applicable.

CCI

CCI

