6.1.1.2. Sensitivity/Supplementary Analyses

CCI

Plots of PK parameters (eg, AUC_{inf} , AUC_{last} , C_{max} , fu , $AUC_{inf,u}$, $AUC_{last,u}$ and $C_{max,u}$) versus hepatic function at baseline (e.g. serum albumin, prothrombin time or total bilirubin, plotted separately) will be constructed, with a regression line and 90% confidence region included from the main linear regression model.

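### Does the `clcr` regressor in the SAP's example regression code mean the wrong analysis of PK against hepatic function will be run?

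*SAP*

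**What the plan says.** SAP 5.2.4 treats hepatic function as a continuous explanatory variable, "using either continuous serum albumin, prothrombin time or total bilirubin, each modelled separately", and sends the reader to Appendix 1 for sample SAS code. SAP 6.1.1.2 plans plots of the PK parameters "versus hepatic function at baseline (e.g. serum albumin, prothrombin time or total bilirubin, plotted separately"), with the fitted line and a 90% region. Protocol 9.3.2.3 describes the same supplementary analysis as relating PK to "hepatic function (eg, serum albumin concentration, PT or T bili").

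Appendix 1 of the SAP has three code blocks: a PROC MIXED ANOVA, a PROC REG linear regression and a PROC GLMSELECT stepwise selection. The PROC REG model line is "model l&var=clcr/clb alpha=0.1". The stepwise block uses albumin, age and weight.

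For the primary comparison, SAP 5.2.3 says "Estimates of the adjusted mean differences (Test - Reference), and corresponding 90% CIs, will be obtained from the model". The matching code line is "lsmeans group/diff cl alpha=0.1", which names no control group.

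**The concern.** A programmer who follows the cross-reference from 5.2.4 finds code that fits a different covariate from the one the text asks for. No visible text defines `clcr`. The usual reading is creatinine clearance, and the nearest mention in the protocol is in the kidney safety appendix: "AE grading for decline in kidney function (ie, eGFR or eCrCl) will be according to KDIGO criteria". That is a grading rule for adverse events, not an analysis covariate.

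Run literally, the block would either fail because the variable is missing or return a slope and R-squared for a kidney measure where a liver measure was planned. The fitted line for the 6.1.1.2 plots would then be missing or wrong.

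The ANOVA block raises a similar worry. If the groups are coded 1 to 4 and no control is named, the default pairwise differences subtract the later level from the earlier. The planned rows would then come out as Reference minus Test, and the ratios would be inverted unless someone reversed them.

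**Working it through.** There is no planned figure to reproduce, so the check sets text against code.

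**Regressor**

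| Place | Explanatory variable |
|---|---|
| SAP 5.2.4 | albumin, prothrombin time or bilirubin, one per model |
| SAP 6.1.1.2 | the same three, as examples |
| Protocol 9.3.2.3 | the same three, as examples |
| SAP Appendix 1, PROC REG | `clcr` only |
| SAP Appendix 1, PROC GLMSELECT | albumin, age, weight |

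The PROC REG block contains 0 of the 3 planned markers. Its other numeric setting agrees with the text: alpha = 0.1 gives 1 - 0.1 = 90% limits, as 5.2.4 requires.

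**What would happen in practice**

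1. The block cannot run as printed. The response and the output data set names contain an unresolved macro variable, `&var`, so the programmer has to edit or wrap it and needs 5.2.4 to know what to fit.
2. Protocol Appendix 2 (Table 5) lists serum creatinine, cystatin C and eGFR, but no creatinine clearance. Protocol 10.7.1 computes eGFR from the combined creatinine-cystatin equation. Unless someone adds a variable called `clcr` to the PK data set, the step stops with an error.
3. If such a variable did exist, the saved parameter table would carry its name beside the slope. A check against 5.2.4 would show that it is not a liver marker.
4. The block saves parameter estimates, fit statistics and the ANOVA table only. The plotted line and 90% region need further code whichever regressor is used, so the plots do not hang on this name.

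Other text also points to a leftover. The stepwise block in the same appendix uses a hepatic marker. The SAP abbreviation list has an entry for amount excreted, which no visible section uses. Carry-over from a template for another study is a reasonable inference, though not a proven one.

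**Direction of the ANOVA differences**

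Four groups give 4 x 3 / 2 = 6 pairwise rows, of which 3 are planned. By default the levels are ordered by formatted value and each row is the earlier level minus the later.

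- Coded 1, 2, 3, 4: the planned rows are 1 - 2, 1 - 3 and 1 - 4, which is Reference minus Test.
- Formatted with the output labels in SAP Section 5, the alphabetical order is Mild, Moderate, Severe, Without. The planned rows are then each impaired group minus Without, which is Test minus Reference.

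The SAP does not say which applies, so the code alone does not establish a reversal. Naming '1' as the control would rest on the same unstated coding. SAP 5.2.3 and 6.1.1.1 state in words which groups are Test and which is Reference. If a row does come out reversed, changing its sign restores it: on the log scale the interval has the same width, and the ratio becomes its reciprocal.

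**The case for a change.** The best argument for a change is that 5.2.4 points to this code, that programmers and quality-control staff work from the SAP, and that code cited in a plan should match its text at a cost of one word. The stepwise block does not cure the mismatch, because it is a different analysis and has neither prothrombin time nor bilirubin. A redacted definition of `clcr` would not cure it either, because the visible list of regressors would still differ from the code.

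All of that is correct as description. What fails is the step from mismatch to consequence. The text and the code do not compete as two plausible plans: three sections in two documents name liver markers, and nothing visible proposes creatinine clearance as a covariate. An analyst who notices the difference has only one sensible reading. It can be said that every regression is at risk, but that holds only if the analyst follows the sample line and disregards the section that cites it.

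On the ANOVA, the argument that naming a control is safer coding is fair as a preference. It does not show that the planned output would be wrong.

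**Conclusion.** The inconsistency exists and is clerical: one variable name in one line of sample code. No change to the plan follows. The governing text identifies the regressors, literal use would most likely fail visibly, and the regression is supplementary (Protocol 9.3.2.3 makes it optional). The primary ANOVA, the safety analyses, the sample size and all stated figures are untouched. The ANOVA direction is fixed in words and is not shown to be reversed.

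This rests on two assumptions. One is that the programmer works from SAP 5.2.4 and 5.2.3 and not from the sample code alone. The other is that no blacked-out text plans an analysis on creatinine clearance; nothing visible suggests one. The name can be tidied if the SAP is reopened for another reason, but it gives no reason to reopen it.

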Appendix 2. Categorical Classes for ECG and Vital Signs of Potential Clinical Concern

Categories for QTcF

Absolute value of QTcF (msec)	>450 and \leq 480	>480 and \leq 500	>500
Increase from baseline in QTcF (msec)	>30 and \leq 60	>60	

Categories for PR and QRS

PR (ms)	max. \geq 300	
PR (ms) increase from baseline	Baseline $>$ 200 and max. \geq 25% increase	Baseline \leq 200 and max. \geq 50% increase
QRS (ms)	max. \geq 140	
QRS (ms) increase from baseline	\geq 50% increase	

Categories for Vital Signs

Systolic BP (mm Hg)	min. $<$ 90	
Systolic BP (mm Hg) change from baseline	max. decrease \geq 30	max. increase \geq 30
Diastolic BP (mm Hg)	min. $<$ 50	
Diastolic BP (mm Hg) change from baseline	max. decrease \geq 20	max. increase \geq 20
Seated pulse rate (bpm)	min. $<$ 40	max. $>$ 120

Measurements that fulfill these criteria are to be listed in the report.

Appendix 3. List of Abbreviations

Abbreviation	Term
AE	adverse event
Ae	Amount excreted
ANOVA	analysis of variance
AUC	area under the curve
BLQ	below the limit of quantitation
BP	blood pressure
CI	confidence interval
CL	Clearance
CCI	
C_{\max}	maximum observed concentration
CCI	
CSR	clinical study report
CV	Coefficient of variation
ECG	Electrocardiogram
IP	Investigational Product
LLQ	Lower limit of quantitation
Ln	Natural log
N/A	not applicable
NC	not calculated
ND	not done
NS	no sample
PK	pharmacokinetic(s)
QTc	corrected QT
QTcF	corrected QT (Fridericia method)
SAP	statistical analysis plan
SOA	Schedule of activities
TEAE	Treatment emergent adverse events
CCI
